**Hypotheses:**

- 1a. Participants with LLA will exhibit significantly increased endurance (as evidenced by an ability to walk significantly further in a timed walking test) wearing the mRSF compared to the ESF.
- 1b. Participants will report significantly reduced levels of exertion after performing a timed walking test in the mRSF, compared to the ESF.
- 2a. Participants will report significantly increased mobility, balance confidence, and health and significantly decreased fatigue when using the mRSF, compared to the ESF.
- 3a. Use of the mRSF will significantly reduce participants' net energy cost of walking (ECW) at slow, comfortable, and fast walking speeds, compared to the ESF.

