Participants will be recruited from their local prosthetist's office (Davidson Prosthetics, Federal Way, WA). Davidson Prosthetics is the sole location for recruitment as this is the only provider of the mRSF in the Northwestern United States.

Participants will be asked to come to the University of Washington Assessment and Training Laboratory (ATL) for three test sessions. Participation in the study will require participants attend three visits over the course of about three months, totaling approximately 7.5 hours.

Session 1: At the first session, we will screen participants, explain the study to them, and obtain informed consent (**Appendix 1**). Participants who agree will then be administered a baseline survey and perform initial speed testing. The baseline survey will include non-identifiable, medical, and demographic questions we will use to characterize the study sample (**Appendix 2**). Participants will then be asked to walk on a treadmill for 6 minutes to determine their comfortable walking speed. The treadmill is equipped with full-length handrails that allow the participant to steady him/herself as needed. A researcher will be next to the subject at all times to assist the subject if he or she were to become distressed.

Participants will be given blinded control of the treadmill speed for the first 30 seconds of testing in order to select their preferred speed. Each participant's comfortable speed will be noted and used as a reference for the metabolic testing (see Session 2 and 3, described below). Slow and fast speeds will be self-selected using an identical method (blinded control of the treadmill adjustment). Participants will be asked to perform a 6 minute practice trial at their self-selected fast speed to ensure the participant is capable of sustaining the speed without undo stress. If a participant is unable to sustain the set speed for the entire 6 minutes, he/she may reduce speed as desired, and a weighted average of the start and end fast speeds will be used for treadmill testing in Sessions 2 and 3. We will also give participants a step activity monitor to wear on their prosthesis. The activity monitor is a small, unobtrusive sensor about the size of a pager that is worn on the prosthesis and measures steps taken by the participant while they are away from the lab. Participants will be shown how to attach the activity monitor to their prosthesis by study investigators. Session 1 is expected to take about 1.5 hours.

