Participants will remove the K4b2 monitor and conduct the 6MWT according to the protocol described above. After completing the Borg RPE, the participant will re-don the K4b2 monitor and sit quietly in order to return to their resting VO2 rate.

Participants will begin the treadmill testing once they have returned to their resting VO2 rate.

Participants will walk for 6 minutes on the treadmill at comfortable, slow, and fast walking speeds (as determined in Session 1). The order of the speeds will be randomized within-subjects to control for fatigue. This randomized order will be carried over into the third session so that participants are tested in the same order both times. Walking VO2 consumption rate (ml/min) will be averaged over the final 1 minute period of each activity. Participants will rest at least 5 minutes between each walking trial in order to return to their resting VO2 rate.

Session 2 will require about 3.0 hours to complete. Upon conclusion of Session 2, participants will transition to the second prosthesis (ESF or mRSF, depending upon randomization) and will be asked to use it exclusively for 1 month before returning for Session 3.

Session 3: The third session will be identical to the Session 2, but will be conducted with participants using the alternate prosthesis (e.g., ESF if they were previously tested in the mRSF).

2. Would subjects undergo these or similar procedures (medical, psychological, educational, etc.) if they were not taking part in this research?  No  Yes If "Yes," describe how the study procedures differ from what subjects would otherwise undergo.

The study procedures include outcome measures (survey measures, 6MWT, or Borg RPE) that a prosthetist might perform in a clinic to evaluate a patient's performance with a new prosthesis. However, the Cosmed K4b2 portable metabolic analysis system and treadmill walking are unlikely to occur in normal prosthetic clinical practice. These procedures are more likely to be conducted as part of a physical therapy treatment plan and would not be considered unusual procedures at a physical therapy clinical visit.

3. Check all of the boxes below that apply to your research:

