## E. RISKS AND BENEFITS

In order to approve the research the IRB must find that risks are reasonable in relation to anticipated benefits, if any, to subjects, and the importance of the knowledge that may reasonably be expected to result.

1. Describe nature and degree of risk of possible injury, stress, discomfort, invasion of privacy, and other side effects from all study procedures, drugs and devices (standard and experimental), interviews and questionnaires. Include psycho-social risks as well as physiological risks. Include risks of withholding standard care or procedures if this is the case. Do not reference the consent form.

Participants will be asked to walk for about 70 minutes total for this study (a maximum of 6 minutes at a time, and 30 minutes maximum per session). Because they are being asked to walk, there is the risk that they could become fatigued during the study procedures. In addition, there is a risk of falling. However, these risks are no larger than the risks that study participants generally undertake when walking outside of this study.

2. Explain what steps you will take to minimize risks of harm and to protect subjects' rights and welfare. (If you will include protected groups of subjects (minors; fetuses in utero; prisoners; pregnant women; unviable neonates; neonates of uncertain viability; decisionally impaired or economically or educationally disadvantaged subjects) please identify the group(s) and answer this question for each group. Please also complete the SUPPLEMENT: Protected and/or Vulnerable Populations.)

This study will not require participants to perform activities at a level of endurance that they would not typically do outside of the study session. To minimize risks of fatigue and falling during the study session, the participants will be asked to take breaks after each walking measure is collected. The maximum time that each participant will be asked to walk continuously is 6 minutes. They are also instructed to take a break, including a sitting break, at any time during the data collection session, including in the middle of walking measures. If at any time it appears that the participant is at risk of falling or other harm, the data collection session will be stopped.

3. Is it possible that you will discover a subject's previously unknown condition (disease, suicidal intentions, genetic predisposition, etc.) as a result of study procedures?  No  Yes If yes, explain how you will handle this situation.

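### Does the unspecified weighted average for the fast treadmill speed put participants who slowed in practice at a speed they cannot hold?

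*Protocol*

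**What the plan says.** Section B of the Protocol (Session 1) has participants choose slow, comfortable and fast treadmill speeds with blinded control of the treadmill. The fast speed then gets a check: "Participants will be asked to perform a 6 minute practice trial at their self-selected fast speed", with the aim "to ensure the participant is capable of sustaining the speed without undo stress". If the check fails, there is a fallback: "If a participant is unable to sustain the set speed for the entire 6 minutes, he/she may reduce speed as desired", and then "a weighted average of the start and end fast speeds will be used for treadmill testing in Sessions 2 and 3". Neither the weights nor a repeat trial at the averaged speed is described.

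In the test sessions, "Participants will walk for 6 minutes on the treadmill at comfortable, slow, and fast walking speeds (as determined in Session 1"). Walking oxygen "consumption rate (ml/min) will be averaged over the final 1 minute period of each activity". Hypothesis 3a concerns "net energy cost of walking (ECW) at slow, comfortable, and fast walking speeds, compared to the ESF". Section E.2 lets participants take a break "at any time during the data collection session, including in the middle of walking measures".

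**The concern.** The practice trial exists to show that the fast speed can be held for 6 minutes. The participants who fail that check are the only ones who then receive a test speed they did not walk as such during the check. It is necessarily faster than the speed to which they had slowed. Because the weights are missing, two operators could also derive different speeds from the same practice trial.

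At stake is the fast-speed part of hypothesis 3a. Oxygen uptake is read from the final minute, which is where a speed set too high would show. A fast trial that is slowed or interrupted could leave that value missing or not at steady state. If this happened with one foot only, the within-person pair at that speed would be lost. With a maximum of 24 completers (section D.1), one pair is 1/24, about 4%, of the fast-speed comparison.

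**Working it through.** The Protocol gives no treadmill speeds, no frequency of slowing and no figure to reproduce. The speeds below are assumptions chosen to show the size of the effect.

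**1. Is the average above the end speed?** Let S be the start speed, E the end speed (E < S, since the rule applies only after a reduction) and w the weight on S, with 0 < w < 1. The test speed is v = wS + (1 − w)E, so v − E = w(S − E) > 0. It is above the end speed, and by the same reasoning below the start speed.

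**2. What does time weighting give?** If the participant slows once, after t minutes, then w = t/6 and v = [tS + (6 − t)E]/6. The distance walked in practice is 60 × [tS + (6 − t)E] = 360v metres. The time-weighted average is therefore exactly the mean practice pace. With S = 1.6 m/s:

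| E (m/s) | t (min) | v (m/s) | Distance in 6 min (m) | v above E | Cut if E were used instead | Time held at E (min) |
|---|---|---|---|---|---|---|
| 1.2 | 2 | 1.333 | 480 | 11.1% | 10.0% | 4 |
| 1.2 | 3 | 1.400 | 504 | 16.7% | 14.3% | 3 |
| 1.2 | 4 | 1.467 | 528 | 22.2% | 18.2% | 2 |
| 1.4 | 2 | 1.467 | 528 | 4.8% | 4.5% | 4 |
| 1.4 | 3 | 1.500 | 540 | 7.1% | 6.7% | 3 |
| 1.4 | 4 | 1.533 | 552 | 9.5% | 8.7% | 2 |

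In each row the participant has already covered, in 6 minutes, the distance that the test trial will ask for. What is untested is covering it at a constant speed.

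**3. Does another choice of weights change this?** With equal weights and speeds of 1.6 and 1.2 m/s, v = 1.40 m/s whenever the slow-down comes. Against the mean practice pace that is 1.40/1.267 = 10.5% higher for a slow-down after 1 minute, 1.40/1.333 = 5.0% higher after 2 minutes, equal after 3, and 1.40/1.467 = 4.5% lower after 4. So the average can exceed demonstrated pace, but only if the operator takes a plain mean, which leaves the word weighted with nothing to do.

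**4. Can the rule favour one foot?** The speed is fixed in Session 1 and carried into both test sessions. Whatever weights are used, each participant has one fast speed for the modified running foot and for the energy storing foot. The paired comparison stays at matched speed.

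**5. Would the end speed be a confirmed speed?** No. In the table it was held for 2 to 4 minutes, not 6. It was also chosen freely, so it need not be the highest pace the participant could keep. Session 1 takes place before the month of use of each assigned foot, and the test trials follow a 6-minute walk test and are done with the mask and backpack monitor. Neither rule shows what can be sustained under those conditions.

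**The case for a change.** The strongest case for a change runs as follows. The speed is an experimental condition, needed at the treadmill in Session 1, so an analysis plan cannot supply the weights afterwards. The longer a participant holds the start speed before slowing, the closer the time-weighted value comes to the speed just shown to be too fast. The end speed was at least held to the finish after faster walking. Using it would need no weights, would add no walking time and would cost one sentence. Eligibility (section D.3) requires 6 minutes of continuous walking, but not at the fast speed.

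Much of this stands as description. The weights are absent, the averaged speed is not itself rehearsed, and a trial that fails with one foot only would be a real loss. It does not carry the conclusion. The check does have a consequence, because the speed comes down. The Protocol does not promise a second check at the lowered speed. The end speed can fall well below a sustainable fast pace if a participant is cautious, which moves fast towards comfortable and weakens the three-speed contrast in hypothesis 3a. Between a mean pace actually covered and a freely chosen finishing pace, the investigators' choice is a fair compromise. The allowance for breaks covers all walking measures and does not arise from this rule. Rest of at least 5 minutes between treadmill trials already limits carry-over of fatigue.

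**Conclusion.** No change to the plan is called for. The text does leave the weights open, and the averaged speed does exceed the end-of-practice speed: by 5% to 22% in the assumed examples with time weighting and a slow-down after 2 to 4 minutes. Read in the ordinary way, however, it equals the mean pace covered in practice. It is the same for both feet, so no bias follows, and it may well be sustainable. Harm needs three things in turn: slowing in practice, failing at the lower averaged speed, and losing the final-minute reading. The Protocol gives no rate for any of them. If all three occurred for one participant, the loss would be about 4% of the pairs at one of three speeds.

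Substituting the end speed would exchange one speed not confirmed over 6 minutes for another, at a cost of about 5% to 18% of the fast speed in the same examples. These percentages depend on the assumed speeds and a single step down. The conclusion rests on the time-weighted reading and on the use of one common speed per participant in both test sessions.

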**B. RESEARCH PROCEDURES INVOLVED.**

1. Provide a complete description of: a. the study design, and b. sequence and timing of all study procedures that will be performed, e.g., volume of blood, size of biopsy, drug administration, questionnaire, name of psychological test. Provide this information for each phase of the study (pilot, screening, intervention and follow-up). **Use lay language.** Attach study flow sheet, if available.

We will conduct a study to compare endurance, walking performance, mobility, and perceived exertion of participants with transtibial amputation wearing two different prostheses: (1) a prosthesis with a modified Running Specific Foot (mRSF), and (2) a prosthesis with a Energy Storing Foot (ESF). To maximize study resources, we will recruit participants who will be receiving from their prosthetist the mRSF prosthesis as part of their normal clinical care. We will fabricate a duplicate prosthesis with the ESF as part of this study to be used as a comparison.

*Note: Both the mRSF and ESF included in this study are devices that people with LLA use daily in their normal lives outside of this study. These feet (and other components included in the prostheses created for this study) are class I devices and exempt from U.S. Food and Drug Administration premarket notification procedures.*

We will conduct a randomized crossover study to compare endurance, energy expenditure, and reported health of participants with transtibial amputation wearing prostheses with the mRSF and ESF described above. Study participants will be randomly assigned to the first foot condition (i.e. ESF or mRSF). To standardize test conditions, the participant's prosthetist ([name]) will fabricate two comparable prostheses with identical (i.e. duplicated) prosthetic sockets, interfaces, and suspension mechanisms. The same socket cannot be used for both prostheses because of the unique, direct-lamination attachment of the mRSF to the socket. The duplicate socket will be fitted with common ESF, the Ossur Vari-flex foot. We have obtained written commitments from Ossur to donate prosthetic components and from Davidson Prosthetics to donate time and materials needed to fabricate the duplicate sockets and test prostheses. Participants will be asked to wear the same athletic shoes for all sessions in order to standardized footwear between tests.

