Session 2: The second session will be performed after participants use the randomly-assigned ESF or mRSF prosthesis for a period of 1 month. Upon arrival at the lab, study

staff will remove the activity monitor and ask the participant to complete a self-report survey (**Appendix 2**) to evaluate their perceived performance, health, and satisfaction with their prosthesis. The survey will be administered on a tablet computer (iPad) and includes the following standardized instruments selected to measure participants' mobility, fatigue, balance confidence, activity restrictions, and satisfaction:

- Prosthetic Limb Users Survey of Mobility - PLUS-M measures respondents' self-reported mobility with a prosthesis. The PLUS-M was developed by the investigators in a prior study to address methodological limitations present in existing mobility measures. We will administer the PLUS-M computer adaptive test (CAT) to achieve the greatest precision of measurement and ease respondents' burden (i.e., CAT requires participants answer fewer questions than would taking the entire survey).
- PROMIS - Fatigue - PROMIS-F measures symptoms and effects of fatigue on respondents' ability to execute daily activities over a 1-week recall period. We will also administer PROMIS-F by CAT.
- Activities Specific Balance Confidence Scale - ABC measures respondents' confidence in performing basic ambulatory activities. We will administer a version of the ABC recommended to ease administration and improve scoring. All 16 questions of the ABC will be administered (CAT not available).
- Trinity Amputation and Prosthesis Experience Scales - Revised - TAPES-R is a multidimensional health instrument that measures activity restrictions and satisfaction with a prosthesis. We will administer 19 TAPES-R questions (CAT not available).

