**c. Ethnic and racial minority populations:**

We will not exclude participation based on ethnicity or race.

**3. What characteristics (inclusion criteria) must subjects have to be in this study? (Answer for each subject group, if different.)**

Inclusion criteria include: 18 or more years of age, non-dysvascular unilateral transtibial amputation, prosthetic user for >1 year, are scheduled to receive a prosthesis with a mRSF, able to walk continuously for at least 6 minutes with or without an assistive device, able to read and write English.

**4. What characteristics (exclusion criteria) would exclude subjects who are otherwise eligible from this study? (Answer for each subject group, if different.)**

Exclusion criteria include any health condition that would limit use of a prosthesis (e.g., skin breakdown), ability to safely walk for at least 6 minutes (e.g., heart disease), or participation (current or planned over the study period) in another research study that may affect the fit or function of his/her prosthesis.

**5. Describe the subject recruitment strategies you will use for each group of subjects. (You should obtain letters of cooperation from agencies, institutions, or others involved in subject recruitment for your research records. Do not send these to HSD or the IRB.)**

Study participants will be exclusively recruited from Davidson Prosthetics, the only local prosthetics facility that routinely provides prostheses with ESF and mRSF to people with LLA. Informed consent will be obtained from all participants.

**6. Explain who will approach subjects to take part in the study and how this will be done to protect subjects' privacy. (Attach letters of cooperation from agencies, institutions or others involved in subject recruitment.)**

Flyers will be posted at Davidson Prosthetics with study information and the phone number of the study coordinator (**Appendix 4**). In addition, [name] will let potential participants know about the study and provide the phone number of our study coordinator. Potential participants can call our study coordinator to get more information about the study, decide if they are interested in participating, and schedule their first study session (**Appendix 5**).

**7. Explain what steps you will take during the recruitment process to minimize potential coercion or the appearance of coercion.**

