Their prosthetic care provider ([name]) will only inform potential participants about the study. All recruitment and enrollment procedures will be conducted by study investigators/coordinators. All interested participants will be informed that participation (or not) is completely voluntary and will in no way affect the clinical care they receive. No members of our study team are or will be involved in the clinical care of potential participants or participants.

8. Will you give subjects gifts, payments, services without charge, or extra course credit?  No  Yes If yes, explain:

Subjects will receive \$30 for every hour of participation in the screening session (Session 1). Participants will receive \$50 for every hour of participant in data collection sessions (Sessions 2 & 3). Participants will be paid after each session.

9. Will any of the subjects or their third-party payers be charged for any study procedures?  No  Yes If yes, explain:

N/A

10. **UW Locations and research sites.** Provide the following information in list or table format for all UW locations at which any research procedures will occur. Be sure to consider: screening, recruiting, consenting, observation, intervention, data collection, data analysis, specimen analysis, and location of any consultants and collaborators.

- Geographical location and/or address
- Name of organization, agency, group, site, institution
- What procedures will occur at each location (how the location is involved in the research)
- Whether subject contact or interaction will occur at each site
- Whether consenting of subjects will occur at each site
- Whether each site, or individuals at the site, will obtain, use, or have access to coded or individually identifiable private information about subjects for research purposes

	Site 1:	Site 2:
	University of Washington Department of Rehabilitation Medicine Health Sciences Building, BB tower, 8 th floor	Davidson Prosthetics, LLC [name]
Screening	X (Screening will be done by study investigators/staff over telephone)	
Recruiting	X (The study will be described to potential participants by study investigators/staff. Potential participants will have the opportunity to ask questions and decide if they would like to schedule a data collection session at this time)	X ([name] will post flyers and let potential participants know about the study)

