- The cultural acceptability of the consent process (or documentation)
- Cultures or groups in which it is considered impolite to refuse a request and/or in which people are fearful of refusing requests that they regard as coming from authorities

N/A

4. **Undue influence.** Describe how you will minimize any undue influence on your subjects' decision about participating in your research. If this is not an issue for your research, describe why. *This is an important consideration when persons recruiting or consenting subjects are in a position of authority or influence – for example, the subject's teacher, doctor, or employer.*

Potential participants will be identified via flyers (**Appendix 4**) posted in their prosthetic office. However, all other recruitment and consenting procedures will be

done by study investigators who are not involved in potential participant's health care. Study investigators will stress that participation is voluntary and in no way will participation (or non-participation) in the study affect their prosthetic (or other health) care.

5. **Subject comprehension.** Describe anything that you will do to facilitate or verify your subjects' comprehension of the information you provide them during the consent process.

Potential participants will be encouraged to ask questions throughout the consent process.

6. Do you expect that all of your participants will be **fluent** in spoken and/or written English?  No  Yes.

If "No", please answer the following questions.

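### Does the promise that taking part leaves prosthetic care untouched conflict with the month each participant is assigned to the comparator foot?

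*Protocol*

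**What the plan says.** Protocol section VIII.B.1 describes a randomised crossover in which "we will recruit participants who will be receiving from their prosthetist the mRSF prosthesis as part of their normal clinical care". The inclusion criteria in VIII.D.3 agree: participants "are scheduled to receive a prosthesis with a mRSF". The ESF prosthesis is a duplicate made for the study.

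On wear, the Session 2 description reads "The second session will be performed after participants use the randomly-assigned ESF or mRSF prosthesis for a period of 1 month". At the end of Session 2 participants change to the second prosthesis and "will be asked to use it exclusively for 1 month before returning for Session 3".

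Two assurances appear elsewhere. VIII.D.7, on minimising coercion, says that taking part or not "will in no way affect the clinical care they receive". VIII.I.4, on undue influence, says that "in no way will participation (or non-participation) in the study affect their prosthetic (or other health) care".

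The form's prompt in VIII.E.1 says "Include risks of withholding standard care or procedures if this is the case". The answer deals with fatigue and falls while walking and concludes that "these risks are no larger than the risks that study participants generally undertake when walking outside of this study".

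**The concern.** If the mRSF is a participant's usual care and the study assigns a month on another foot, taking part does appear to alter prosthetic care, whatever the assurances say. The conflict is plainest for someone randomised to the mRSF first, who is asked to wear only the ESF in the second month.

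A second worry is exposure. Exclusive use is stated for the second month but not for the first, and no section says when the mRSF is handed over. If an ESF-first participant already had the mRSF and wore it at times in month 1, the self-reported outcomes of hypothesis 2a would reflect a mixture of feet, and the difference in that sequence would shrink. The risk answer, which does not mention withheld care, then looks incomplete.

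At stake would be the accuracy of what participants are told and some dilution of the self-report comparison.

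**Working it through.** The plan gives no figure to reproduce, so the check is mainly a comparison of sections.

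**1. Assigned foot by month (VIII.B.1)**

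| Sequence | Month 1 | Month 2 |
|---|---|---|
| mRSF first | mRSF | ESF, exclusive use stated |
| ESF first | ESF, use stated | mRSF, exclusive use stated |

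Each participant has one ESF month out of two. The move to the second prosthesis comes only after Session 2, in both sequences. The two session descriptions together therefore give one foot per month. The missing word in month 1 is a drafting difference and does not permit alternating between feet.

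**2. Is there a contradiction about having the mRSF in hand?** VIII.B.1 says participants will be receiving it, VIII.D.3 says they are scheduled for it, and VIII.H.3a says the delivery schedule will be collected from the prosthetist. These statements are compatible. VIII.D.7 and VIII.I.4 say nothing about delivery or possession. Handover timing is left open; the sections do not state it two ways.

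**3. What the assurances mean.** Each answers a question about pressure on potential participants, and each pairs taking part with not taking part. An assurance that covers both choices is about the consequences of the decision: care is not a reward for joining or a penalty for declining. Under VIII.I.1 the study itself is explained separately, from the written consent form, which is not available here. Nothing can be inferred about whether that form describes the ESF month.

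**4. Size of any dilution.** Code a full month on the ESF as 0 and on the mRSF as 1, and assume self-report follows the share of wear linearly. Let q be the share of month 1 that ESF-first participants spend on the mRSF, and r the share of month 2 that mRSF-first participants spend on it.

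- ESF-first difference, Session 3 minus Session 2: 1 − q
- mRSF-first difference, Session 2 minus Session 3: 1 − r
- Equal-weight average: 1 − (q + r)/2

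| q | r | Fraction of true difference |
|---|---|---|
| 0 | 0 | 1.00 |
| 0.1 | 0 | 0.95 |
| 0.2 | 0 | 0.90 |
| 0.5 | 0 | 0.75 |
| 0.2 | 0.2 | 0.80 |

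The first row is the plan as written. Every other row needs a value of q or r that the documents do not supply. Nor is there a reason to set r to zero while q is positive: mRSF-first participants have certainly had the mRSF by month 2 and are only asked to leave it aside. The rows therefore describe ordinary non-adherence, which any take-home crossover can suffer, and not a bias created by the wording.

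**5. Outcomes affected.** The 6-minute walk, perceived exertion and oxygen measurements are taken in the laboratory on the assigned foot. Mixed wear could reach them only through acclimation.

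**The case for a change.** The strongest case for a change is that these sentences describe what participants will be told, so literal accuracy matters, and prosthetic care is exactly what the randomisation assigns. The rest of the application does not make up for it. The answer to VIII.B.2, on how procedures differ from usual care, names the metabolic system and treadmill but not the ESF month. The site table in VIII.D.10 marks intervention as not applicable at both sites. Aligning the sentences would cost little.

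Part of this stands. The assurances are worded more broadly than the design allows, and the two wear descriptions differ by one word. Were the text revised, these are sections to reconcile with one another; the wear rule and handover timing belong to the investigators.

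The argument does not show a consequence. The risk prompt is conditional, and whether it applies is debatable: participants still receive the mRSF, VIII.A describes the ESF as the foot commonly prescribed to active users, and VIII.B.1 notes that both feet are in daily use outside the study. For ESF-first participants, usual care is displaced only if the mRSF would otherwise have been worn during month 1, which no section establishes. The dilution argument needs an assumed share of wear, a linear response, and lapses in one sequence only.

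**Conclusion.** No change to the plan is called for. The mismatch is real on a literal reading and touches one of two wear months for each participant, up to 24 people. It is a matter of wording in answers about coercion. The sequence of assigned feet is clear enough for staff to run the study and for analysts to know which foot each session represents. With the plan followed as written the effect on the estimates is zero; the figures of 0.95 to 0.75 hold only under assumed wear shares of 10% to 50% in one sequence.

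This conclusion rests on reading the two session descriptions together as one foot per month, and on taking the assurances in the context of the questions they answer. It makes no claim about the consent form, which is not available here. Handover timing is a practical detail that those running the study can be expected to settle.
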